### **2.3.2 Part II: Economic Analyses**

#### **2.3.2.1 Primary Objective**

To evaluate the cost-effectiveness of AM-PICC vs S-PICC.

#### **2.3.2.2 Secondary Objectives**

**To evaluate:**

1. The direct hospital costs of using AM-PICC compared with S-PICC over 6 months from randomisation.
2. The cost-effectiveness of AM-PICC compared with S-PICC over the participants' expected lifetime from the perspective of the NHS.
3. The potential value of additional research to reduce any uncertainty observed in the cost-effectiveness model. This will be used to inform decisions about long-term follow up of the trial cohort.
4. The value of implementing the cost-effective intervention (AM-PICC vs S-PICC) throughout the NHS in England and Wales.

5. The costs of a BSI to the NHS.

## **2.4 Potential Risks and Benefits**

### **2.4.1 Potential Risks**

As the control and intervention arms of the trial are similar in so many respects, the risks of intervention are confined to those attributable to the antimicrobial coating of the AM-PICC. The actual dose of antimicrobials and the slow release which is believed to occur mean that even if total systemic bioavailability were to occur, the foreseeable disadvantage to a baby would be less than receiving a single systemic dose of either active ingredient. Thus adverse drug reactions are likely to be rare and unlikely to be serious and should not prevent the trial from proceeding.

A second possible risk of participation could be the emergence of resistant organisms (34). However, rifampicin resistance is unlikely to be clinically significant as rifampicin is only very rarely used in neonatal practice and rifampicin resistance does not confer resistance against other classes of antibiotics (35).

Colonisation with rifampicin resistant organisms may be confined to the device as the serum level of rifampicin remote from the indwelling device will be very low. It is possible that bacteria at the entry site might become resistant to rifampicin, and similarly that fungal species with resistance to miconazole might emerge. If colonisation with resistant organisms does occur, there is no reason to believe that such resistant organisms should have higher virulence than other skin commensal organisms which might colonise the line site. If resistant organisms do colonise the line and, if these organisms give rise to BSI, antibiotics commonly prescribed for presumed line infections would be expected to be efficacious.

### **2.4.2 Known Potential Benefits**

Ten percent of all babies are admitted to NNU (68,000 per year in England) and around 6% of these develop one or more BSI. Very preterm babies (<32 weeks gestation) account for 10-15% of admissions to NNU but 53% of NNU care days and (58%) of total BSI in NNU (6-8). BSI occurs in 5-20% of very preterm babies, mostly in association with PICC or other central venous catheters (CVCs). The consequences of BSI include death, increased duration of intensive care and permanent neurological impairment. Hence, strategies to prevent BSI could have enduring health benefits and reduce long-term health and welfare costs.

Based on evidence in older children and adults, antimicrobial impregnation of PICC appears promising for very preterm babies, but specific evidence is needed for this population. Several cost-effectiveness analyses of impregnated lines have been published, but all focus on adult patients (21-24). A UK analysis showed that even very small reductions in absolute BSI rates would be cost-effective (as low as 0.2%) (14, 21).

## **PART I: RANDOMISED CONTROLLED TRIAL**

### **3 SELECTION OF SITES/CLINICIANS**

Trial sites will be initiated once all governance (e.g. local R&D approval) and trial-specific conditions (e.g. training requirements) have been met, and all necessary documents have been returned to MC CTU. Initiation meetings will cover the requirements outlined in CTRC SOPs TM017 and TM018.

It will be expected that all sites selected will follow good clinical standards with particular attention to aseptic practise and infection monitoring. For example, use nationally recommended asepsis procedures (0.5% chlorhexidine and will take a minimum of 0.5ml of blood for any blood culture).

#### **3.1 Site/Clinician Inclusion Criteria**

The trial will take place in NNUs in England. Any NNU can participate providing they obtain approval as a Recruiting Site or Continuing Care Site (CCS).

##### **3.1.1 Recruiting Sites**

Prioritisation for site inclusion will be given to the 5-6 largest NNU's providing level 2 and 3 care within 3 neonatal networks (Yorkshire and Humber, North East North Central London and Trent). Other sites will be invited to participate through the Children's Clinical Research Network.

Training in the protocol requirements and the requirements outlined in CTRC SOPs TM017 and TM018 will be disseminated to personnel at a trial launch meeting and continually on site for all relevant new staff who may be involved in the trial.

Adherence to the protocol procedures will be monitored throughout the trial by the Trial Coordinator/Data Manager. Participating sites will be expected to maintain a file of essential trial documentation (Investigator Site File), which will be provided by the MC CTU, and keep copies of all completed CRFs for the trial.

##### **3.1.2 Continuing Care Sites (CCS)**

CCS will be required to gain R&D approval in order to follow-up the participant.

#### **3.2 Site/Clinician Exclusion Criteria**

Not meeting the inclusion criteria listed above.

## 4 TRIAL DESIGN

### 4.1 Primary Endpoint

The primary endpoint will be time to first BSI based on a positive blood/CSF culture (any positive bacterial or fungal blood/CSF culture will be included) taken between 24 hours after randomisation until 48 hours after removal.

As part of the primary endpoint there will be two sensitivity analyses:

1. A sensitivity analysis confined to clinically serious BSI defined by positive culture and the baby is treated for more than 72 hours with intravenous antibiotics or dies during treatment.
2. Time to first BSI based on a positive blood culture (including fungal BSI) taken between 24 hours after PICC insertion until 48 hours after removal.

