The disadvantage of a PICC is the increased risk of BSI. Bacteria or fungi stick onto the inside or around the tube and multiply. In babies with immature immunity, infection spreads via the blood stream, causing sepsis and infecting other organs. Treatment requires intravenous antibiotics for at least 5 days and sometimes antifungals are required. BSIs occur in 5-20% of babies born before 32 weeks of gestation (unpublished data from audit of 5 NNUs), mostly in association with central venous catheters. The consequences can be serious and include death, increased duration of intensive care, and in the longer term, permanent neurological impairment, even when BSI is due to less pathogenic skin organisms (9). Although intensive antibiotic treatment for BSI may be lifesaving, it also carries risks. Intensive antibiotic treatment alters the microbial ecology of the gut, which may increase the risk of necrotising enterocolitis (NEC) (10-12). NEC involves severe inflammation of the intestine and can result in necrosis of large sections of the bowel. Strategies to prevent BSI are therefore important to help babies who need a PICC avoid these serious and costly consequences (13).

There are 45 published randomised controlled trials (RCTs) of central venous catheters that have been impregnated with antiseptics or antimicrobial substances to prevent BSI, but none have been conducted in very preterm babies (14). Antibiotic impregnation was investigated in 7 RCTs and was one of the most effective interventions with an average 80% reduction in catheter-related BSI (odds ratio 0.18; 95%CI 0.08-0.34). The 7 RCTs were all confined to

adults. All used catheter-related BSI as the primary outcome, which could overestimate the effect of impregnation due to contamination of culture media with antibiotic from impregnated catheter tips. A further RCT has recently been completed of children in UK paediatric intensive care units comparing minocycline-rifampicin impregnated central venous catheters (Fr 4 or 5) with standard catheters. Heparin-bonded catheters are included as a third arm in this trial. The median duration of catheters was 2.5 days and the median age was 6 months (personal communication from trial investigators).

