## **5.4 Participant Withdrawal**

In consenting to the trial, participants are consented to the trial intervention, follow-up and data collection.

The Parent/legal representative is free to withdraw consent from the entire trial (including the intervention) at any time prior to PICC insertion without providing a reason.

Once the PICC has been inserted it will only be removed when clinically indicated. Clinically indicated removal includes but is not limited to: PICC no longer needed or expected adverse outcomes such as thrombosis, infection, or PICC displacement. Once the PICC is removed for whatever reason – this should be recorded on Form 6:Removal.

The Parent/legal representative is free to withdraw consent for follow-up and data collection at any time without providing a reason.

Sites should explain the value of remaining in trial follow-up, or failing this, of allowing routine follow-up data to be used for trial purposes. It should therefore, if possible, be clarified with the Parent/legal representative the level of follow-up and data collection they would like to withdraw from.

A withdrawal CRF will then be completed and any further data will be collected for the trial as per the parent/legal representative's wishes.

Data up to the time of withdrawal will be included in the analyses unless the participant explicitly states that this is not their wish. If this occurs, contact should be made with the MC CTU to discuss and an additional withdrawal CRF (for withdrawal of data) will be provided for completion.

If a parent/legal representative decides to withdraw consent, regardless of the level of withdrawal, data for Health Episode Statistics and Data linkage will not be sought.

When withdrawn, the participant will receive appropriate care under medical supervision until the symptoms of any adverse events resolve or the participant's condition becomes stable. Blood/CSF cultures and PICC tip culture will still be undertaken if clinically indicated and deemed necessary as part of routine clinical care. In line with usual clinical care, decisions as to the clinical management of the baby will be made by the attending clinical team in conjunction with parent/legal representative.

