## 6.5 Clinical Follow-up – starting at Randomisation

The following information will be captured on Form 4: Daily Follow-up which should be completed for each day from randomisation until 48 hours after randomised PICC removal / attempted insertion / randomisation if not attempted as per table 1 section 8.2. It may be completed retrospectively but it must be completed regularly (at a minimum of every 7 days). It should be completed as at 23.59 on the specified dates.

- Randomised PICC status (in situ/removed/etc)
- PICC tip culture taken (if applicable) – Form 5: Microbiology also needs updating
- Blood/CSF cultures samples taken – Form 5: Microbiology also needs updating
- Antibiotics/Antifungals
- Related adverse events – Form 8: Related AEs also needs updating

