## **7.5 Concomitant Medications**

Use of antibiotic and antifungal medications will be recorded at from 72 hours before randomisation and documented throughout trial participation until the baby has reached the end of the clinical follow up for primary outcome (see section 8.2).

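### The 72-hour treatment criterion for clinically serious BSI cannot be verified for late BSIs, because antimicrobial recording ends 48 hours after line removal

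*Protocol*

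**What the plan says.** Protocol 4.1 counts any positive bacterial or fungal blood/CSF culture "taken between 24 hours after randomisation until 48 hours after removal". Its first sensitivity analysis is confined to clinically serious BSI: a positive culture where "the baby is treated for more than 72 hours with intravenous antibiotics or dies during treatment".

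Antimicrobial use is captured as follows:

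- **Section 6.5.** Antibiotics and antifungals are an item on Form 4, which "should be completed for each day from randomisation until 48 hours after randomised PICC removal / attempted insertion / randomisation if not attempted".
- **Section 7.5.** "Use of antibiotic and antifungal medications will be recorded at from 72 hours before randomisation" and is then "documented throughout trial participation until the baby has reached the end of the clinical follow up for primary outcome". Table 1 in 8.2 sets that end at 48 hours after line removal, after the last attempted insertion, or after randomisation if nothing was attempted.
- **Section 8.1.** The schedule marks review of antimicrobials under baby characteristics and daily follow-up only, not at line removal or discharge.
- **Section 6.6.** The Form 7a items reviewed at transfer, discharge, death or 26 weeks include milk intake, NEC, retinopathy and parenteral nutrition, but no antibiotics.

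**The concern.** The criterion looks forward from the culture by more than three days. The record stops at the moment the last qualifying culture can be taken. A baby sampled on the day of removal has at most about two recorded days of treatment left, and a baby sampled at the very end of the window has none.

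The protocol suggests that this will not be rare. Section 2.1 says of BSI that "Treatment requires intravenous antibiotics for at least 5 days", so treatment courses will often outlast the record. Section 5.4 counts among the clinical reasons for removal "expected adverse outcomes such as thrombosis, infection, or PICC displacement", so some BSIs will themselves bring removal forward and cut their own record short.

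At stake is a robustness check. The primary endpoint accepts any positive culture in an unblinded trial, and this analysis is meant to show whether the result holds for infections treated as real. If an unverified duration is read as a criterion not met, late BSIs are classed as not serious whatever treatment they received.

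**Working it through.** **Notation.** R is the time of line removal, S the time of the positive sample, and L the hours of treatment already given when the sample was taken. The record ends at R + 48 h (6.5, 7.5, Table 1).

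**Treatment that can be recorded** = (R + 48) − S + L.

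**Condition for more than 72 h:** (R + 48) − S + L > 72, that is, S < R − 24 + L.

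Recordable hours if treatment starts at the sample (L = 0):

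| Sample time | Recordable treatment | More than 72 h? |
|---|---|---|
| R − 24 h | 72 h | no |
| R | 48 h | no |
| R + 24 h | 24 h | no |
| R + 48 h | 0 h | no |

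If earlier treatment counts, the latest classifiable sample moves to just before R (L = 24), R + 24 h (L = 48) or R + 48 h (L = 72). Form 4 is completed once per day, as at 23.59, so these boundaries are accurate only to about a day.

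**Babies without an inserted line.** With no attempt, the record ends 48 h after randomisation and the first qualifying culture is at 24 h. At most 48 − 24 = 24 h of treatment is visible with L = 0. With a failed attempt at the 48-hour limit, the record ends at 48 + 48 = 96 h, leaving at most 96 − 24 = 72 h, which is still not more than 72.

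**Share of the sampling window affected.** For a dwell of D days with insertion at randomisation, the window runs from 24 h to 24D + 48 h, so its length is 24D + 24 hours. The last 72 h are affected when L = 0. Under a constant hazard the share is 72 / (24D + 24) = 3 / (D + 1). Section 9.4 gives a median dwell of 10 days and means of 10 to 29 days.

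| Dwell | Window | Share affected | Of 79 BSIs (9.4) |
|---|---|---|---|
| 10 days | 264 h | 72/264 = 27% | about 22 |
| 20 days | 504 h | 72/504 = 14% | about 11 |
| 29 days | 720 h | 72/720 = 10% | about 8 |

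The last column counts positive-culture BSIs falling in the affected period. Not all of them would be serious under complete recording.

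These rows fix one dwell for every baby. If dwell instead varied exponentially with a median of 10 days, the share pooled over all babies would be about 19%, which lies inside the same range.

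**Deaths.** Death is recorded on Form 7a up to discharge or 26 weeks (6.6; Table 4 in 10.1). For a death after R + 48 h the date is known, but whether antibiotics were still running is not.

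**The case against.** A reader might infer that no BSI sampled within a day of removal or later could ever be called serious. The documents do not support that. The definition has a second limb, death during treatment, and deaths are recorded past the cut-off. Section 8.3 expects some cultures in babies already on antibiotics, and 7.5 records antimicrobials from 72 hours before randomisation, so a late BSI can reach the threshold if prior treatment counts. The protocol does not say whether it does.

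It can also be said that the form fields are not shown. Table 8 in 10.2.6 sends suspected or confirmed BSI to Form 5 and Form 6, and 10.4 follows adverse events to resolution. This is fair as a caution, but none of these places names antibiotic duration, and 7.5 states directly when recording of antimicrobials ends. The start of the 72-hour clock may reasonably be left to the statistical analysis plan. Data that were never collected cannot be supplied there.

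Two further inferences go too far. This is not the only analysis bearing on contamination, since organism type and catheter-related BSI are secondary endpoints in 4.2. Nor can a loss of power be computed for it. That would need the share of BSIs that prompt removal within a day and the share that are truly serious. The protocol gives neither, and 9.4 powers only the primary comparison.

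A bias between arms is possible if removal after suspected infection differs by line type, but 8.4 asks sites to treat babies alike, and the documents give no basis for its direction or size.

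**Conclusion.** The point stands in limited form. For BSIs sampled from 24 hours before removal onward, the duration criterion cannot be verified on the planned record unless treatment began before the sample. For deaths after the cut-off, whether the baby was still under treatment is also unrecorded.

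The affected share of the sampling window is about 10% to 27% over the dwell times the protocol quotes. That rests on a constant hazard, insertion at randomisation and treatment starting at the sample. It would be larger if BSI prompts removal, by an amount the protocol does not allow one to calculate.

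The primary endpoint, its test and its sample size are untouched. One planned check on an any-positive-culture endpoint would misclassify late BSIs as not serious, which is worth correcting because the remedy is small.

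**What to change.** In 6.5 and 7.5, add that for each baby with a positive blood/CSF culture in the primary window, antimicrobials (drug, route, start and stop) continue to be recorded until that course ends, more than 72 hours of treatment is documented, or the baby dies, even when this falls later than 48 hours after removal. For a culture at R + 48 h with treatment starting then, the record must reach beyond R + 120 h. Mark the extension in the 8.1 schedule, and complete it retrospectively from the notes for babies already followed.

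In 4.1, state when the 72 hours start, including whether treatment before the sample counts, and that both the duration and treatment at death are assessed on the extended record.

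The cost is a short amendment, guidance for the form, and a few extra days of chart review for each culture-positive baby, whose notes are already reviewed for Form 7a. Only data capture changes; care does not.

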### 4.2 Secondary Endpoint(s)

Outcomes captured up until 48 hours after PICC removal:

1. Rifampicin resistance in any isolate from blood/CSF culture.
2. Rifampicin resistance in any isolate from PICC tips.
3. Type of organism isolated from BSI.
4. Rate of BSI per 1000 PICC-days (including recurrent BSI).
5. Occurrence of 1 or more BSI.
6. Rate of catheter-related BSI per 1000 PICC days.
7. Rate of blood/CSF culture sampling per 1000 PICC days.
8. Duration of antimicrobial exposure from randomisation up to 48 hours after line removal.
9. Time to PICC removal.

Outcomes captured up until discharge home from neonatal care/death/6 months post randomisation:

10. Chronic lung disease 36 weeks postmenstrual age.
11. Necrotizing enterocolitis (NEC): Bell's stage II or III.
12. Treatment for retinopathy of prematurity.
13. Abnormalities on cranial ultrasound.
14. Time to full milk feeds after randomisation.
15. Total duration of parenteral nutrition from randomisation until discharge from NNU.
16. Death:
  - a) within 6 months (26 weeks) of randomisation
  - b) before discharge home from neonatal care
  - c) Time to death

For health economics outcomes, please refer to Part II: Economic Analysis.

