#### **2.3.1.2 Secondary Objectives**

**To determine the effect of AM-PICC vs S-PICC on:**

1. Rifampicin resistance in isolates from blood/CSF cultures.
2. Rifampicin resistance in isolates from PICC tips.
3. Type of organism isolated from BSI.
4. Measures of BSI (rate of BSI per 1000 PICC-days (including recurrent BSI), occurrence of 1 or more BSI, rate of catheter-related BSI per 1000 PICC days).
5. Rate of blood/CSF culture sampling per 1000 PICC days.
6. Duration of antimicrobial exposure from randomisation up to 48 hours after line removal.
7. Time to PICC removal.
8. Occurrence of Chronic Lung Disease.
9. Occurrence of necrotizing enterocolitis (NEC): Bell's stage II or III.
10. Occurrence of cranial ultrasound abnormality.
11. Requirement for treatment for retinopathy of prematurity.
12. Time to full milk feeds.
13. Duration of parenteral nutrition from randomisation until discharge home from neonatal care/death/6 months post randomisation.
14. Death:
  - a) Within six months (26 weeks) of randomisation;
  - b) Before discharge home from neonatal care.
  - c) Time to death

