**For all participants who have a PICC inserted within 48 hours from randomisation:**

**At PICC removal**, the attending clinical staff/RN will routinely take a PICC tip culture according to standard clinical practice.

A detailed SOP version 1.0 dated 05/03/2015 on handling and culturing premechath line tips will be disseminated to site's microbiology laboratories.

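### Catheter-related BSI is compared between arms although the protocol itself names a bias in it that favours impregnated lines, and tip-isolate resistance is exposed to the same mechanism if it is analysed per positive isolate

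*Protocol*

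**What the plan says.** Section 2.1 reviews seven adult trials of antibiotic-impregnated catheters, all with catheter-related BSI as primary outcome. It warns that this measure "could overestimate the effect of impregnation due to contamination of culture media with antibiotic from impregnated catheter tips".

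Section 2.3.1.2 nevertheless sets as objectives the effect of AM-PICC versus S-PICC on the "rate of catheter-related BSI per 1000 PICC days" (objective 4) and on "Rifampicin resistance in isolates from PICC tips" (objective 2). Section 4.2 turns these into item 6, "Rate of catheter-related BSI per 1000 PICC days", and item 2, "Rifampicin resistance in any isolate from PICC tips".

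On the tip itself, section 8.3 says that staff at removal "will routinely take a PICC tip culture according to standard clinical practice", whichever arm the baby is in. An SOP "on handling and culturing premechath line tips will be disseminated to" the site laboratories; it is not reproduced. Section 9.6 uses a threshold of p = 0.05 or less for all analyses.

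The protocol does not define catheter-related BSI (the summary in section 1 calls it PICC related BSI). Nor does it fix the denominator for item 2.

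**The concern.** Only the AM-PICC carries rifampicin and miconazole. If residue from its tip reaches the culture medium, growth from that tip can be suppressed in the laboratory although the line was colonised in the baby. An endpoint that needs a positive tip would then miss cases in one arm only, and the AM-PICC rate would look lower than it is. Section 2.1 describes this mechanism, and section 4.2 adopts the measure without referring to it.

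The same mechanism could act on item 2 in the opposite direction. If susceptible organisms fail to grow from AM-PICC tips and resistant ones do grow, the resistant fraction of what grows is inflated. Section 2.1 does not say this; it is an inference.

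Benefit and resistance both bear on adoption. Section 2.2 lists concern about antibiotic resistance among the reasons why UK units do not use these lines. A nominally significant result on either item could be quoted in that debate although part or all of it came from the assay. Growth lost in the laboratory cannot be restored by a statistical method, so the remedy lies in how the endpoint is defined and reported.

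**Working it through.** The documents give no figure for carry-over, so there is none to reproduce. The check sets the text side by side and then illustrates the size under stated assumptions.

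**Which endpoints depend on the tip**

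- Primary endpoint (4.1), and BSI rate and occurrence (4.2, items 4 and 5): cultures of blood or CSF, with blood drawn from a new peripheral site (8.3). They do not use the tip.
- Item 1, resistance in blood/CSF isolates: does not use the tip.
- Item 2, resistance in tip isolates: uses the tip by definition.
- Item 6, catheter-related BSI: dependence on the tip is inferred from the warning in section 2.1, because no definition is given.

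**Assumptions for the illustration**

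- True colonisation, true resistance and PICC days are equal in the two arms (no real effect).
- r = share of tip organisms that are rifampicin resistant. Assumed 5%, range 5-20%.
- f = share of susceptible AM-PICC tips made falsely negative. Assumed 25-50%, range 10-75%.
- Resistant organisms are not suppressed, S-PICC tips are unaffected, and item 6 requires a positive tip.

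**Formulas**

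- Apparent rate ratio for item 6 = r + (1 - r)(1 - f)
- Apparent resistant share among AM-PICC isolates = r / [r + (1 - r)(1 - f)]
- Resistant tips per cultured tip, or per baby: unchanged, ratio 1.0

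**Central case, r = 5%**

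- f = 25%: rate ratio = 0.05 + 0.95 × 0.75 = 0.7625; resistant share = 0.05 / 0.7625 = 6.6%.
- f = 50%: rate ratio = 0.05 + 0.95 × 0.50 = 0.525; resistant share = 0.05 / 0.525 = 9.5%.

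**Range**

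| f | Rate ratio, r = 5% | Rate ratio, r = 20% | Resistant share, true 5% | Resistant share, true 20% |
|---|---|---|---|---|
| 10% | 0.905 | 0.92 | 5.5% | 21.7% |
| 25% | 0.7625 | 0.80 | 6.6% | 25.0% |
| 50% | 0.525 | 0.60 | 9.5% | 33.3% |
| 75% | 0.2875 | 0.40 | 17.4% | 50.0% |

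For scale, the sample size in section 9.4 is built on a fall from 0.14 to 0.07, a ratio of 0.50. Under the assumptions, 50% suppression alone would bring item 6 close to that (0.525) with no real effect. For item 2, the distortion is confined to the per-isolate denominator.

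**The case against.** The strongest reply is that the design has already acted on the warning. Section 2.1 criticises trials that used catheter-related BSI as their primary outcome. Here it is secondary, the primary endpoint does not use the tip, and resistance in blood/CSF isolates is already the first secondary objective. This stands. It limits the point to two secondary endpoints and leaves the main effectiveness claim untouched.

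A second reply is that neutralising carry-over is laboratory method and belongs in the tip SOP, and that the definition of catheter-related BSI may be in the SAP. Neither document is at hand. This also stands as a limit: the protocol's silence does not show that the step was omitted. It does leave the reader of sections 2.1 and 4.2 with a named bias and no pointer to how it is handled.

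Third, item 2 refers to any isolate, which can naturally be read as yes or no per baby, and section 9.6 analyses outcomes on all randomised participants as far as practicable. On that reading the illustrated bias disappears. Section 2.4.1 also treats resistant colonisation of the device as a possible risk in its own right, so resistance that truly arises on the line is what item 2 is meant to detect. Both arguments are sound. What remains is that the denominator should be fixed, because the per-isolate reading is not excluded.

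A reader might go further and infer that neither endpoint can answer its objective, or that the protocol admits that carry-over distorts resistance results. The documents do not support this. The warning is conditional and concerns catheter-related BSI only. Because the expected bias in item 6 runs one way, a finding of no benefit would still be informative.

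**Conclusion.** The point holds for item 6, and conditionally for item 2.

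**Item 6.** The protocol names a bias in catheter-related BSI that favours impregnated lines. It then compares that measure between an impregnated and a plain line, under a 0.05 threshold, with no safeguard in its text. This rests on item 6 requiring a positive tip, which is inferred.

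**Item 2.** Resistance in the AM-PICC arm would be overstated if it were analysed as a share of positive tip isolates, and not on the illustrated mechanism if analysed per cultured tip or per baby.

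**Size.** It is unknown. With 25-50% suppression of susceptible AM-PICC tip growth and 5% resistance, both assumed, a null rate ratio would read about 0.76-0.53 and the resistant share 6.6-9.5% against 5%. These figures show what could happen and are not estimates for this trial. The primary endpoint and items 1, 4 and 5 are unaffected.

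**What to change.** In sections 2.3.1.2 and 4.2:

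1. Define catheter-related BSI and say whether it needs a matching tip culture.
2. If it does, report item 6 descriptively, with tip-culture positivity by arm beside it. State that it cannot by itself support effectiveness, and rest conclusions on BSI on the primary endpoint and items 4 and 5.
3. Do not replace the tip criterion with the clinician's reason for removal. The trial is unblinded (brown staining identifies the AM-PICC) and removal is a clinical judgement, so that criterion could be influenced by knowledge of the allocation.
4. Analyse item 2 per cultured tip or per baby, in the categories no growth, susceptible only and any resistant, and not per positive isolate. Rest the resistance conclusion mainly on item 1.
5. If the tip SOP already neutralises carry-over, cite it for that purpose in place of the restriction on item 6.

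The cost is a change of wording. Culture results and resistance profiles are already recorded on Form 5. The downside is that one secondary endpoint loses its formal test.
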